### **2.1. Sample Size Considerations**

Sample size calculations are based on 80% Power, using a two-sided Pearson's Chi-square Test for Proportion Differences at the 5% significance level. It is estimated that between 60% and 70% of hospitalized patients with mild or severe disease will improve clinically and become ambulatory after standard treatment (WHO ordinal scale score 1-2 Fig.2)). Table 1 presents the sample sizes that are required in each treatment group to detect a significant difference in the percent of hospitalized patient leading to an ambulatory disease (shift from category 5-8 to category1-2 in 20%, 25%, 30% or 35% of hospitalized patients after treatment with estradiol (E2) and progesterone (P4)). Efforts will be made to recruit 60 patients in each treatment group in order to stratify by disease severity, age and gender.

Table 1.		
Treatment	Percent leading to a scale 1-2	Sample Size
SOC	60%	32
SOC + E2 + P4	90%	32
SOC	60%	22
SOC + E2 + P4	95%	22
SOC	70%	62
SOC + E2 + P4	90%	62
SOC	70%	36
SOC + E2 + P4	95%	36

An interim analysis will be performed at 50% enrollment to determine to what extent a strong treatment efficacy warrants stopping the trial early. Table 2 presents interim sample sizes and required Z test statistics for comparing two proportions at each of stage of a O'Brien-Fleming alpha-spending sequential design (24). Based on 80% power and an overall 5% significance level, if the interim analysis for the first 60 enrolled patients results in differences that are more than 2.96 standard deviations from 0, the trial will end, and treatment efficacy will be concluded. Otherwise, the trial will enroll the total 120 patients.

Table 2.			
	Treatment	Sample Size	Standardized Z test Statistic
Stage 1	SOC	30	2.96
	SOC + E2 + P4	30	
Stage 2	SOC	60	1.96
	SOC + E2 + P4	60	

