#### **Secondary outcomes:**

For all randomized patients, the following secondary end points will be assessed at day 14, 28 and 60

1. Length of hospital stay
2. Duration of mechanical ventilation
3. Cause of death and number of days death occurred after admission
4. Readmission
5. Change in biological markers below between admission and occurrence of primary endpoint (2 values at least 2 days apart)
6. Grade 3 and 4 adverse events
  
7. Serious adverse events

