### **3.4 Statistical Analysis**

For all randomized patients according to section 2.2, clinical outcomes and demographic characteristics will be summarized and presented separately for the treatment group and the control group, as well as overall for all patients. Categorical variables such as the primary outcome, readmission, as well as race and sex will be summarized with counts and percentages. Quantitative outcomes, such as length of stay, change in biological markers, age and BMI will be summarized with means, medians, standard deviations, and interquartile ranges. Univariate analyses will be performed as the primary method to assess the unadjusted effect of treatment on the primary outcome and on readmission rate using the Pearson Chi-square test. Differences in average length of stay and in change in biological markers will be assessed with either a two-sample t test or the Mann-Whitney nonparametric test. Multivariate analyses will be performed to compare treatment to control responses while adjusting for various co-factors. Multiple logistic regression will be used as supportive method to test for significant differences in the proportion with the primary outcome, between the active treatment and placebo-equivalent groups, while adjusting for age, race, sex, bmi and other potential co-factors. For the secondary outcomes. multiple logistic regression will also be used to test for significant differences in the proportion readmits, between the active treatment and placebo-equivalent groups, and multiple linear regression will be used to test for significant differences in average length of stay and changes in biological markers, between the treatment and SOC groups, while adjusting for potential influencing co-factors.

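### The marker analysis fixes neither the test, the scale nor adjustment for the admission value, which gives up precision on the trial's routine measure of its mechanism

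*Combined protocol and SAP*

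**What the plan says.** Secondary outcome 5 in section 3.3 is defined as "Change in biological markers below between admission and occurrence of primary endpoint (2 values at least 2 days apart"). The routine markers listed there are the neutrophil:lymphocyte ratio, C-reactive protein, ferritin, procalcitonin, D-dimer, fibrinogen, troponin, two transaminases and LDH.

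Section 3.4 plans two analyses of these changes:

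- **Unadjusted.** Length of stay and "change in biological markers will be assessed with either a two-sample t test or the Mann-Whitney nonparametric test". No rule for choosing is given.
- **Adjusted.** "multiple linear regression will be used to test for significant differences in average length of stay and changes in biological markers". The covariates are described only in general terms. For the primary outcome, by contrast, age, race, sex and BMI are named.

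Section 3.4 makes the unadjusted analysis the primary method for the primary outcome and for readmission. For the markers it does not say which analysis leads. No transformation is mentioned, and no power statement covers the markers.

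**The concern.** These markers are positive concentrations or ratios, and most can be expected to have long right tails. If change is taken on the raw scale, a few patients with very high admission values dominate the comparison. A plain change score also carries the full noise of the admission value, although that value is in hand for every patient who has a change score.

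The trial's rationale is immunomodulation, and these markers are its routine readout. With test, scale and covariates all open, either result is hard to read: a null finding may reflect an inefficient analysis, and a positive one may reflect the choice made among several analyses.

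**Working it through.** **1. The plan's own figures.** The only sample-size figures concern the binary primary outcome: "Sample size calculations are based on 80% Power", "using a two-sided Pearson's Chi-square" "Test for Proportion Differences at the 5% significance level". For 70% against 90%, with pooled variance and no continuity correction:

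n = [1.96·√(2·0.8·0.2) + 0.8416·√(0.7·0.3 + 0.9·0.1)]² / 0.2² = (1.1087 + 0.4610)² / 0.04 = 61.6, so 62 per arm.

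That matches Table 1, and the other rows (32, 22, 36) reproduce too. Nothing comparable exists for the markers. The checks below borrow the two-sided 5% level and the target of 60 per arm ("Efforts will be made to recruit 60 patients in each treatment group"). Log SD, correlation, effect size and any common fall are assumptions.

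**2. Variance on one common scale.** With equal SD s at both times and correlation rho:

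- change score: variance 2s²(1−rho)
- adjusted for the admission value: variance s²(1−rho²)
- ratio: (1+rho)/2, that is 0.60, 0.65, 0.75, 0.85 and 0.90 at rho 0.2, 0.3, 0.5, 0.7 and 0.8

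For a true effect of 0.5 SD and 60 per arm, power (change score against adjusted) is 58% v 80% at rho 0.2, 64% v 82% at 0.3, 78% v 89% at 0.5, 94% v 97% at 0.7, and 99% v 99.5% at 0.8. For 0.3 SD it is 25% v 39% at rho 0.2 and 38% v 48% at rho 0.5.

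**3. Skewed markers.** Simulated log-normal markers, 60 complete pairs per arm. A common fall means that later values halve in both arms before any treatment effect.

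| Log SD, rho, reduction on treatment | Common fall | t test, raw change | Mann-Whitney, raw change | Log ANCOVA |
|---|---|---|---|---|
| 1.0, 0.5, 40% | none | 41% | 61% | 88% |
| 1.0, 0.5, 40% | 50% | 18% | 34% | 89% |
| 1.0, 0.3, 40% | none | 34% | 48% | 83% |
| 1.0, 0.3, 40% | 50% | 15% | 28% | 83% |
| 0.8, 0.5, 30% | none | 42% | 55% | 81% |
| 0.8, 0.5, 30% | 50% | 17% | 27% | 80% |
| 0.5, 0.5, 30% | none | 90% | 92% | 99% |

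The log ANCOVA column can be checked by hand. In the first row the effect is ln 0.6 = −0.511 and the residual SD is √(1−0.25) = 0.866. So SE = 0.866·√(2/60) = 0.158, z = 3.23, and power is about Φ(3.23−1.96) = Φ(1.27) ≈ 90%, close to the simulated 88-89%.

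The fall matters because it shrinks the raw difference. With log SD 1 and admission median 1, mean values are e^0.5 = 1.65. A 40% reduction is then worth 0.4·1.65 = 0.66 without a fall and 0.33 with one, while the admission noise is unchanged. A ratio on the log scale is unaffected.

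**4. Scale and covariate separately.** In the first row, a t test on log change has about 79% power. Regressing raw change on treatment and the raw admission value has about 66%. Both fall between the planned tests and log ANCOVA, so both choices contribute.

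**5. The open choice of test.** With no treatment effect and log SD 1, taking the smaller of the two p-values rejected in about 7-8% of simulated trials, against a nominal 5%.

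**The case against.** A reader might infer that the plan makes no adjustment for the admission value. The documents do not support that. The linear regression in section 3.4 neither names nor excludes it, and for the markers that regression is not ranked below the simple tests. If the admission value enters, the treatment estimate on a given scale is the same as ANCOVA on the later value. What remains is that its inclusion, and the scale, are not prespecified.

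A reader might also infer that a real anti-inflammatory effect would probably be missed. That is not supported either. The documents give no marker SD, correlation or effect, and power for the planned tests runs from 15% to over 90% across the assumptions above. For a 0.3 SD effect at rho 0.5 or below, adjustment on a common scale also leaves power under 50%. The lowest figures need both strong skew and a common fall. A fall is plausible if the second value is taken at recovery, but the documents do not quantify it.

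Three further points are fair:

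- The raw scale is inferred; the text says only change.
- Offering two tests may mean choosing by distribution. Selection by p-value is possible, not shown. It would also raise power slightly, so it is a separate harm and not a reason why effects would be missed.
- All power figures assume complete pairs. Laboratory values are used only when available, and the second value is tied to reaching the primary endpoint. Section 2.1 expects "between 60% and 70% of hospitalized patients with mild or severe disease will improve clinically". Read strictly, that is 0.6·60 = 36 to 0.7·60 = 42 control pairs. At 30 per arm, a 0.5 SD effect and rho 0.5, power is 49% (change score) v 61% (adjusted).

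**Conclusion.** The point holds as a gap in prespecification with a measurable cost. Test, scale and admission-value covariate are all left open for the markers, and a more efficient analysis is available from data already collected.

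On a common scale the adjusted variance is 60-90% of the change-score variance for rho 0.2 to 0.8. For strongly skewed markers (log SD 1, rho 0.5, 40% reduction, 60 pairs per arm), log ANCOVA gains about 88−61 = 27 points over Mann-Whitney on raw change with no common fall, and 89−34 = 55 points if markers halve in both arms. For a mildly skewed marker with no fall the gain is 99−92 = 7 points; a common fall would widen it. Log ANCOVA had the highest power in every non-null skewed-marker setting tried.

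These sizes rest on assumed values. The markers are one of seven secondary outcomes, so the primary conclusion is unaffected. The change is worth making because it is cheap and concerns the trial's mechanism.

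**What to change.** In section 3.4:

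- Make the main analysis of each marker a linear model of the log later value on treatment and the log admission value, plus any covariates listed by name. Report the ratio of geometric means with its 95% confidence interval.
- State how values below the detection limit enter the log scale.
- Remove the choice between t test and Mann-Whitney for the markers. If a rank test is kept, label it a sensitivity analysis.
- Name one test for length of stay in advance, since the same sentence leaves it open.

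The cost is a few sentences, settled before unblinding. No new data are needed, because the model uses the two values that a change score already requires. It does not solve the timing of the second value, which depends on outcome and is undefined for patients who never reach score 1 or 2. Nor does it solve missing pairs. Both need their own rules.

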### **3.3 Outcome Measures**

For all randomized patients according to section 2.2, demographic and clinical variables, including sex, age, race/ethnicity, BMI, symptoms, vital signs (blood pressure, respiratory rate, temperature, oxygen saturation), chronic comorbidities through diagnosis codes, medications, clinical course during hospitalization (described in primary outcome below) will be reviewed in the patients' medical charts. Laboratory measurements including when available CBC, blood chemistry, liver function test, creatinine, BUN, lactate, troponin, ferritin, CRP, procalcitonin, Brain-type natriuretic peptide, D-dimer, interleukin-6, G6PD. We will review the participants' medical records for up to 6 months after hospital discharge.

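### The supportive logistic model puts an open covariate list on 21–30 expected failures: at the planned effects its odds ratio is overstated by about 13–30% or more, and it can be infinite, most often after an early stop

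*Combined protocol and SAP*

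**What the plan says.** Section 3.4 makes the unadjusted Pearson chi-square the primary analysis of the day-28 responder proportion. A multiple logistic regression is added as a supportive test of the same proportion, "while adjusting for age, race, sex, bmi and other potential co-factors". The section does not close the list, say how race is coded, restrict covariates to those known before randomization, or say what happens if the likelihood has no finite maximum. Readmission gets the same kind of model.

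Section 2.1 supplies the planning rates. On standard care, "It is estimated that between 60% and 70% of hospitalized patients with mild or severe disease will improve clinically"; the treated arm is put at 90% or 95% in Table 1. On size, "Efforts will be made to recruit 60 patients in each treatment group", with the stated aim of stratifying by severity, age and gender. Severity is not among the four covariates that section 3.4 names. Section 2.1 also allows an efficacy stop at 30 per arm if the test statistic exceeds 2.96.

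**The concern.** The information in a logistic model is limited by the rarer outcome, which here is failure to reach score 1 or 2. If the treatment works as well as Table 1 assumes, failures are few and most are in the control arm. Ordinary maximum likelihood then pushes the log odds ratio away from zero, more so with each added term, and gives no finite treatment estimate if nobody in the treated arm fails.

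At stake is the adjusted estimate that readers will set beside the primary result. It would look stronger than the truth in exactly the case the sponsor hopes for, and after an early stop it may not be reportable. Because the list is open, the size of the problem is also open.

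**Working it through.** **1. Table 1 reproduced.** Inputs from section 2.1: "using a two-sided Pearson's Chi-square Test for Proportion Differences at the 5% significance level" and "Sample size calculations are based on 80% Power". Per-arm n = [1.96·√(2p̄(1−p̄)) + 0.842·√(p₁(1−p₁) + p₂(1−p₂))]² / (p₂−p₁)². For 70% v 90%: (1.109 + 0.461)²/0.04 = 61.6, so 62. The four pairs give 32, 22, 62 and 36, matching Table 1.

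**2. Expected failures at 60 per arm** = 60(1−p_c) + 60(1−p_t):
- 60/90: 24 + 6 = 30
- 60/95: 24 + 3 = 27
- 70/90: 18 + 6 = 24
- 70/95: 18 + 3 = 21

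With no effect the count is 36 (70% in both arms) to 48 (60% in both).

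**3. Terms in the model.** Treatment, age, sex and BMI are four slopes. Race adds one (two levels) to three (four levels), making 5 to 7. Failures per slope run from 21/7 = 3.0 to 30/5 = 6.0, before any further covariate.

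**4. Bias of maximum likelihood, by simulation at 60 per arm.** The documents give no covariate effects, so two sets of assumptions were used.

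*Set A*: independent standard normal covariates, four with log-odds 0.4 per SD and the rest null, intercepts set to the Table 1 marginal rates. Median odds ratios:

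| Rates | True | 4–6 covariates besides treatment | 10 covariates |
|---|---|---|---|
| 70/90 | 4.4 | 5.0–5.1 | 5.5 |
| 60/95 | 15.8 | 20–21 | 24.5 |

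That is 5.0/4.4 = 1.14 up to 21/15.8 = 1.33, and 5.5/4.4 = 1.25 up to 24.5/15.8 = 1.55. A separate run of the same set-up gave 27–60% with 10 covariates, so these ranges are approximate.

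*Set B*: race in two levels, or in four (50/35/10/5%); moderate covariate effects (log odds ratio −0.3 to −0.5); 3,000 trials per setting. Inflation = exp(median − true log odds ratio) − 1. For example, at 60/90 with two-level race: exp(2.045 − 1.910) − 1 = 14%.

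| Rates | Named, race 2 levels | Named, race 4 levels | Four extra, race 4 levels (10 covariates) |
|---|---|---|---|
| 60/90 | 14% | 18% | 36% |
| 60/95 | 14% | 24% | 51% |
| 70/90 | 9% | 12% | 24% |
| 70/95 | 14% | 23% | 38% |

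Coverage of the 95% interval was 0.95–0.98 with the named covariates and 0.915 at worst with eight extra. At 70/80 the bias was about 4–9%. At 70/70 there was none, and the rejection rate was 4.7–6.2%.

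**5. No treated failure at full enrolment** = p_t^60. 0.90^60 = 0.2%; 0.95^60 = 4.6%.

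**6. The same at the interim look.** Exact enumeration of two binomials of 30, stopping when the pooled Z exceeds 2.96 (Table 2):

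| Rates | Chance of stopping | Mean failures if stopped | No treated failure if stopped | Product |
|---|---|---|---|---|
| 60/90 | 40% | 15.8 | 10% | 4% |
| 60/95 | 68% | 14.1 | 30% | 20% |
| 70/90 | 14% | 13.1 | 22% | 3% |
| 70/95 | 34% | 11.8 | 45% | 15% |

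The last column (chance of stopping × chance of no treated failure given a stop) is the share of all trials that stop early with an infinite treatment odds ratio.

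**7. Firth-penalised fit.** Under set A the median odds ratio stayed within about 5% of truth at 70/90 and 60/90, and was about 8–12% low at 60/95. Under set B the mean log odds ratio was within about −1% to +2% of truth.

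**The case against.** The strongest reply is that little depends on this model. It is declared supportive, it is used to test rather than to estimate a named quantity, and the primary chi-square, sample size and stopping rule do not use it. With only the named covariates, interval coverage is close to nominal and the test holds its level. The 21–30 failures also presuppose effects of 20 to 35 points; a smaller effect brings more failures and less bias. All of this stands, and it limits the weight of the point.

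It is also fair that removing race and BMI would be a preference rather than a correction. A penalised fit tolerates them, so they need not go.

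Two further inferences are tempting. Section 3.3 lists "medications, clinical course during hospitalization (described in primary outcome below" among the chart data, and some standard-care drugs depend on oxygen need, so a reader might infer that the model will adjust for consequences of treatment. The plan does not say so: that list describes data collection, and section 3.4 merely fails to rule it out. A reader might also infer that readmission is sparser still, but the documents give no readmission rate.

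The reply does not answer the early stop. There the model rests on about 12–16 failures, and the plan has no fallback for an infinite estimate.

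**Conclusion.** The concern holds as an inexpensive improvement to a supportive analysis. At the Table 1 effects, the adjusted odds ratio from ordinary maximum likelihood is overstated by about 13–30% with the named covariates (9–24% under the second set of assumptions) and about 25–55% with 10. Non-existence is rare at full enrolment (0.2–4.6%) but common in a trial stopped for efficacy (about 10–45%).

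A reader might infer that the adjusted odds ratio is bound to be inflated or undefined, or that the model manufactures false positives. Neither follows. There is no bias under no effect, only a few per cent at 70/80, and the null rejection rate is near 5%. The bias exaggerates a large effect; it does not create one.

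The failure counts and the zero-failure and interim probabilities need only the Table 1 rates and the Table 2 boundary. The bias sizes also depend on assumed covariate distributions and effects, and the figure of 10 covariates is an illustration, since the plan gives no number.

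**What to change.** In section 3.4:

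- Replace the open ending of the covariate list with a short fixed list, all measured before randomization: baseline WHO score (3–5), age and sex. Race and BMI may stay if coded compactly, with the coding stated.
- Fit the model by Firth-penalised logistic regression with profile-likelihood confidence intervals.
- Report the standardized risk difference with its 95% CI beside the odds ratio.
- Use the same method for readmission if it is modelled.

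Baseline score is already an entry criterion, and severity is already a stratification aim in section 2.1, so no new data are needed. The cost is a few sentences and a few lines of code, plus slight shrinkage of the odds ratio when the effect is very large. The primary test and the sample size do not change.

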### **3.5 Data Storage**

All data and research files will be de-identified and stored using the secure web application Research Electronic Data Capture (REDCap). REDCap is protected by a login as well as encryption. There is also an audit trail, which tracks all logins and activities in the database. All data for this study will be electronic; there will be no paper records. Enrolled subjects will be assigned a sequential study ID (i.e. 001, 002, etc) that is linked to their medical record number. A link between the study ID numbers and medical record number will be kept in a separate file from the de-identified database and stored securely in REDCap. Only the IRB-approved study investigators will have access to the data and link. The password-protected study log will be destroyed three years after the study is complete.

## **4. Risks**

This is a greater than minimal risk study due to the new investigational use of an FDA-approved drug in this study. IM injection may cause some swelling and tenderness at the injection site. The side effects of estradiol includes breast tenderness. The side effects of progesterone include vaginal bleeding. In

addition, drawing blood from a vein may cause local pain, bruising, occasional lightheadedness, dizziness, fainting, and very rarely, infection at the site of the blood draw. To reduce risk of anxiety or pain related to the blood draw, experienced nurses or phlebotomists will draw blood.

The risk of deep vein thrombosis (DVT) or pulmonary embolism associated with estradiol and progesterone treatment exists but is minimal. First, the risk of DVT is associated with chronic hormone therapy, over months, not acute hormone therapy of several days. Most importantly, the risk is minimal because of parenteral estradiol administration, which does not alter clotting factors. DVT risk occurs mainly following orally administered estrogens and synthetic progestin because of first-pass liver metabolism leading to high liver exposures to hormones that increase hepatic production of clotting and inflammatory factors (19). Additionally, the DVT risks are usually associated with the use of conjugated equine estrogens (Premarin) alone or associated with a synthetic progestin like medroxyprogesterone acetate (Prempro) (19). There is no documented risk with natural hormones estradiol given systemically (IM, SC) and no documented risk with the use of progesterone. Additionally, most COVID-19 patients are at risk of DVT and will be placed on prophylactic anticoagulants at admission as Tulane SOC.

There is a risk of breach of confidentiality. In order to minimize this risk, all data will be de-identified and minimal PHI will be gathered (i.e., medical record number). Maintaining a link between the study ID number and medical record number is important to prevent a given chart being entered twice in the database. PHI will be stored securely in REDCap and separately from the study dataset.

A schedule of risk assessment is shown on Fig.1

